5.4.8. Duration of AEs

Duration of Adverse events (days) will be calculated as follows: (Event End date – Event Start date) + 1.

For the events that are ongoing at end of study, date of end of study will be considered as Event End date.

5.4.9. Laboratory Abnormalities

The standard laboratory results will be compared against the standard low/high ranges reported.

If result < the low range, then, the result will be flagged as 'Low'. If the result is > the high range then, the result will be flagged as 'High'. Otherwise, the result is between the low and high ranges and will be flagged as 'Normal'.

Minimum and Maximum post-baseline abnormalities will also be flagged for each subject.

For urinalysis parameters, the results will be categorized as 'Normal' and 'Abnormal'.

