2.2 Endpoints

2.2.1 Safety Endpoints

- Type, frequency, severity, duration, and relationship to study drug of any AEs and laboratory abnormalities graded according to CTCAE version 4.03

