4.2. Study Endpoints

4.2.1 Safety Endpoints

Type, frequency, severity, duration, and relationship to study drug of any AEs and laboratory abnormalities graded according to the National Cancer Institute Common Terminology Criteria for Adverse Events (CTCAE) version 4.03.

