6.10.2. Clinical Laboratory Evaluations

Clinical laboratory assessments will include hematology, chemistry, coagulation, and urinalysis. Analysis will be performed by the central laboratory. The laboratory evaluation schedule is shown on the Schedule of Assessments (Appendix 13.1).

A descriptive summary of the laboratory results along with change from baseline will be provided.

Shift in clinical laboratory evaluations will be summarized by low, normal and high.

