6.10.2.2. Serum Chemistry

A descriptive summary of the chemistry results along with the change from baseline will be presented. The following laboratory tests will be performed:

[REDACTED]

Liver Function Tests ALT and AST will be presented separately. Other chemistry parameters will be presented separately.

The shift table of liver function tests will be summarized by cohort group for the following categories based on the maximum value of AST and ALT of any post-baseline assessments relative to their baseline categories:

- 1 – 1.5x upper limit of normal (ULN)
- >1.5 – 2.0x upper limit of normal (ULN)
- >2.0 – 3x upper limit of normal (ULN)
- >3.0 – 5x upper limit of normal (ULN)
- >5x upper limit of normal (ULN)

Shift in abnormality in chemistry values other than ALT and AST will be summarized by minimum and maximum post-baseline abnormal category. Clinical laboratory evaluations will be summarized by low, normal and high.

A listing will present chemistry values for all subjects.

In Mock Shell: Table 14.3.3.2, Table 14.3.3.3, Table 14.3.3.7, Table 14.3.3.8 and Listing 16.2.8.2

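### The safety endpoint calls for CTCAE-graded laboratory abnormalities, but no SAP laboratory rule assigns a grade, and the ALT/AST shift table has no category for a normal value

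*SAP*

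**What the plan says.** The endpoint is the same in both documents. Protocol 2.2.1 covers AEs and "laboratory abnormalities graded according to CTCAE version 4.03". SAP 4.2.1 repeats this with the full name of the criteria: "laboratory abnormalities graded according to the National Cancer Institute Common Terminology Criteria for Adverse Events (CTCAE) version 4.03".

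The SAP's derivation rule for laboratory data is in 5.4.9: "The standard laboratory results will be compared against the standard low/high ranges reported". Values below the range are flagged Low. For the upper side the text reads "If the result is > the high range then, the result will be flagged as" High, and everything else is Normal. Urinalysis results are Normal or Abnormal.

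The general laboratory summary in SAP 6.10.2 follows the same scheme: "Shift in clinical laboratory evaluations will be summarized by low, normal and high". The same section says of these tests: "Analysis will be performed by the central laboratory".

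ALT and AST have their own shift table in SAP 6.10.2.2, "based on the maximum value of AST and ALT of any post-baseline assessments relative to their baseline categories". It lists five bands in multiples of ULN, the lowest running from 1 to 1.5x.

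Protocol 6.4.2 and footnote 11 of the Schedule of Assessments allow dosing only once local-laboratory ALT and AST are within the normal range.

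**The concern.** The safety endpoint serves the primary objective. If the SAP is followed as written, its laboratory part is not analysed in the form in which it is defined. A High flag does not separate a marginal excursion from a severe one, which is what a grade is for.

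The remaining route to a grade is the AE form. SAP 6.10.1.2 rates AEs by CTCAE and tabulates TEAEs by severity and cohort. Graded laboratory results would then depend on recording practice at about 5 sites, even though the values come from a central laboratory and could be graded uniformly.

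The ALT/AST table matters because transaminase elevation is the liver signal that the protocol follows most closely. A shift table that cannot place a normal baseline, or a subject who stays normal, does not show the whole cohort.

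**Working it through.** The plan gives no figure to reproduce, so the check is a side-by-side reading followed by simple counts.

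**1. Does any SAP laboratory rule assign a CTCAE grade?**

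| SAP section | Scale used | CTCAE grade assigned |
|---|---|---|
| 5.4.9 | Low / Normal / High; urinalysis Normal / Abnormal | No |
| 6.10.2 | Descriptive summary, change from baseline, low / normal / high shift | No |
| 6.10.2.1 Hematology | Low / normal / high shift on minimum and maximum | No |
| 6.10.2.2 Chemistry | ALT/AST in ULN multiples; other analytes low / normal / high | No |
| 6.10.2.3 Urinalysis | Normal / abnormal shift | No |
| 6.10.2.4 Coagulation | Descriptive summary and listing | No |

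Panels with a planned graded table: 0 of 4 (hematology, chemistry, urinalysis, coagulation). The ULN bands are not labelled as grades or mapped to them. Whether they match CTCAE cut-points cannot be judged, because the CTCAE tables are not in the documents.

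**2. How complete is the AE route?** Protocol 7.0 asks for abnormal results to be recorded as AEs. The next sentence refers to results that worsen and are clinically significant in the investigator's judgment, and Protocol 6.2.4 has the investigator classify each abnormal result in that way. Protocol 7.0 also exempts findings associated with the underlying disease unless they are more severe than expected. Protocol 1.1 says A1AT deficiency is associated with liver disease in some people, so the exemption could be applied to a liver test. Because chronic liver disease is excluded at entry, that is possible rather than certain.

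**3. How many laboratory sets are involved?** The protocol visit sections and schedule give post-dose safety laboratory sets on Days 1, 2 and 7 and at Weeks 4, 12, 24 and 52, which is 7 per subject. SAP 6 excludes Cohort 4 and Part B, leaving Cohorts 1 to 3. Assume 2 to 5 subjects in each and no replacements:

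- Subjects: 3 × 2 = 6 to 3 × 5 = 15.
- Sets: 6 × 7 = 42 to 15 × 7 = 105.

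These are all scheduled sets. The number that will hold an abnormality not recorded as an AE is unknown.

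**4. What does the ALT/AST shift table cover?** The bands are 1–1.5, >1.5–2.0, >2.0–3, >3.0–5 and >5x ULN. Bands below 1x ULN: 0 of 5.

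- Baseline: the dosing rule puts the local value at or below 1x ULN. A central-laboratory baseline could differ, but normal is what the protocol requires, and any baseline below ULN has no listed category.
- Post-baseline: a subject whose maximum stays below ULN has no listed category either.
- A value exactly at ULN is Normal under 5.4.9, because High requires exceeding the range, but it falls in the 1–1.5x band of 6.10.2.2.
- SAP 5 uses the full cohort as the percentage denominator, so the listed rows need not add up to it.

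**5. Over how many draws is each maximum taken?** Protocol 6.4.8 has two draws a week from Day 7 to Week 14: 98 − 7 = 91 days = 13 weeks, and 13 × 2 = 26. Single draws at Weeks 15, 16, 18, 20, 24, 28, 32, 40 and 52 add 9, for a total of about 26 + 9 = 35. Protocol 3.9 instead starts the twice-weekly draws at Day 1, with the end point redacted, so 35 is approximate.

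**The case against.** The strongest reply is that laboratory abnormalities are graded through the AE route. The opening sentence of Protocol 7.0 on abnormal results is broad, and the sentence on investigator judgment can be read as an illustration rather than a limit. Protocol 7.2 sends AEs found in laboratory data to the AE page, and Protocol 7.3.2 says to report when in doubt. SAP 6.10.1.2 then keeps the most severe occurrence by cohort. The endpoint also lists duration and relationship to study drug, which are collected for AEs and not for raw laboratory values. Protocol 8.3.1 promises no graded laboratory table.

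Much of this stands. Laboratory changes recorded as AEs will have a worst grade by cohort, so the gap is confined to abnormalities that are not recorded. But the endpoint names laboratory abnormalities alongside AEs. Reading them as only those that became AEs makes the phrase redundant, and leaves the grade to site practice.

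On the shift table, the bands include the protocol's own thresholds of 1.5x, 2x and 5x ULN. The never-elevated count could be found by subtraction, and every value is listed. That makes this part a minor table correction, but the SAP still defines no category for a normal value. Its Missing row is for dropouts and missing values.

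The mock shells are not in the documents, and SAP 6.10.2.1, 6.10.2.2 and 6.10.2.5 are partly redacted. A shell may hold a grade or a normal row. No legible rule defines either.

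**Conclusion.** The concern holds: the stated endpoint and the planned laboratory analysis do not match. In the legible SAP text, 0 of 4 panels has a CTCAE-graded table and 0 of 5 ALT/AST bands lies below 1x ULN. Between 42 and 105 scheduled post-dose laboratory sets, under the cohort-size assumption above, would be graded only where a site recorded an AE.

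The consequence is limited to reporting. Raw values, extremes and reference-range flags will still be available, and DLT and suspension decisions are unaffected. No sample size, alpha or power is involved. The endpoint mismatch carries the weight and should be corrected; the shift-table gap alone would be minor. The conclusion assumes that the redacted text and unseen shells add no grading rule and no normal category.

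**What to change.** In SAP 5.4.9, add a CTCAE v4.03 grade derived by program for each gradable analyte. Tabulate worst post-baseline grade and shift from baseline grade by cohort, alongside the existing Low/Normal/High flags.

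In SAP 6.10.2.2, add a first category of ≤1x ULN for both the baseline and the maximum post-baseline value, and start the next band at >1 to 1.5x ULN. This gives normal values a row and removes the conflict at exactly 1x ULN. The other bands can stay as they are.

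The cost is SAP wording, one derived variable from data already collected, and one or two tables. No trial procedure changes.

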5.4.10. PCS Abnormalities Criteria: ECG

The criteria for potentially clinically significant (PCS) abnormalities are shown in the following table:

ECG: Criteria for PCS Abnormalities
Ventricular Rate (Beats/Min) 
• <45• >100
P-R Interval (msec) 
• <100• >200
QRS Duration (msec) 
• < 80• > 200
Q-T Interval (msec) 
• <250• >500
Q-Tc Interval (msec) 
• <250• >500

5.4.11. PCS Abnormalities Criteria: Vital Signs

The criteria for clinically relevant vital signs abnormalities are shown in the following table:

Vital Signs: Criteria for PCS Abnormalities
Systolic Blood Pressure 
• <90 mmHg• >180 mmHg
Diastolic Blood Pressure 
• <50 mmHg• >100 mmHg
Temperature 
• <36 ° C• >38 ° C
Heart Rate 
• <40 beats per minute• > 100 beats per minute
Respiratory Rate 
• <12 breaths per minute• >20 breaths per minute

5.4.12. Protein Augmentation Therapy (PAT) at baseline

PAT use at baseline (washout of at least 8 weeks from last PAT dose and baseline) will be flagged as below.

- Subjects with prior use of PAT at baseline
- Subjects without prior use of PAT at baseline

The following medications are considered Protein Augmentation Therapy (PAT) with trade names Glassia, Prolastin-C, Aralast NP or Zemaira and generic name: Alpha1-proteinase Inhibitor (human).

5.4.13. [REDACTED] A1AT Data

[REDACTED]

Result derivations:

- If the result for an individual pool is [REDACTED], then it is considered as a positive result.
- Cumulative result is calculated by subtracting the medium control individually from the positive samples and then by adding only the positive responses.

6. Statistical Analyses

All summaries will be presented by cohorts and total. All summaries will be presented for FAS population.

All data listings will be presented as collected in CRF. All listings will be based on FAS population, unless specified.

Based on the safety and efficacy data from Part A, and in consultation with the Study Principal Investigators, the study did not proceed to Part B and will be excluded from all the analyses.

IV Cohort 4 was not enrolled due to sponsor's decision and will be excluded from all the analyses.

6.1. Subject Disposition

A summary of disposition of subjects will include the number and percentage of subjects for the following categories but not limited to: subjects screened, subjects treated (FAS population), subjects completing DLT observation period and completing the study, discontinued from the study and primary reason for discontinuation.

The reasons for subjects not completing the study include:

- Lost to follow-up
- Withdrawal of consent for participation in the study
- Adverse event(s) that put the safety of the subject at risk

- Major protocol deviation prior to treatment. The Investigator should discuss the protocol deviation with the Medical Monitor before withdrawing the subject
- Investigator decides to discontinue the subject
- Sponsor decides to discontinue the subject.
- Other

Subject disposition information will be listed by dose cohort and subjects.

A summary of screen failures includes subjects who failed to meet eligibility criteria at screening and baseline visits with corresponding reasons for screen failure. Any discontinuation/withdrawal prior to dosing is considered a screen failure. Percentages will be based on all subjects screened.

Inclusion / Exclusion criteria will be listed for all subjects screened.

In Mock Shell: Table 14.1.1.1, Table 14.1.1.2, Listing 16.2.1 and Listing 16.2.3.4

6.2. Significant Protocol Deviations

A summary of significant protocol deviations will include number and percentage of subjects with any significant protocol deviation along with their categories.

All protocol deviations reported will be listed by dose cohort and subjects. All the significant protocol deviations will be listed separately along with their impact on the analysis and corresponding mitigation action items.

In Mock Shell: Table 14.1.2, Listing 16.2.2.1 and Listing 16.2.2.2

6.3. Demographics and Baseline characteristics

A summary of demographic and baseline characteristics will include the following parameters:

- Age
- Sex
- Ethnicity
- Race
- Height (cm)
- Weight (kg)
- BMI (kg/m²)

Subject demographics information will be listed by dose cohort and subject.

In Mock Shell: Table 14.1.3 and Listing 16.2.3.1

6.4. Disease Characteristics

A summary of disease characteristics at baseline will include the following parameters:

- A1AT genotype
- Prior use of Protein Augmentation therapy*

*The following medications are considered Protein Augmentation Therapy (PAT) with trade names Glassia, Prolastin-C, Aralast NP or Zemaira and generic name: Alpha1-proteinase Inhibitor (human).

A1AT genotype results collected at screening will also be listed by dose cohort and subject.

In Mock Shell: Table 14.1.4 and Listing 16.2.3.2

6.5. Medical History

A summary of medical history will include number and percentage of subjects with any medical history. This summary will also include number and percentage of subjects with medical history by system organ class and preferred term.

All medical history information will be listed by dose cohort and subject.

In Mock Shell: Table 14.1.5 and Listing 16.2.3.3

6.6. Other Screening data

Chest X-Ray results and Hepatic Ultrasound Observations Results collected at screening will be listed by dose group and subject.

In Mock Shell: Listing 16.2.8.9 and Listing 16.2.8.10

6.7. Prior and Concomitant medication

Concomitant medications include all prescription drugs, herbal products, vitamins, minerals, and over-the-counter medications used between signing the informed consent form (ICF) and the End-of-Study Visit (EOS).

Verbatim terms for prior and concomitant medications are to be coded using the World Health Organization Drug Dictionary (September 2017).

A summary of prior/concomitant medications will include number and percentage of subjects with any prior/concomitant medication and the total number of prior/concomitant medications. This summary will also include number and percentage of subjects with the corresponding medication by Therapeutic Main group (ATC Level 2) and preferred term.

Prior and concomitant medications will be presented separately.

Prohibited concomitant medications include protein augmentation therapy (PAT) for the treatment of alpha-1 antitrypsin deficiency for 3 months following treatment with IMP (Day 0) or other investigational therapies.

After the Week 12 visit, the treating physician in consultation with the Medical Monitor may decide to resume or start PAT, based on clinical judgment as well as data from study participation. Subjects who resume or start PAT post-treatment will remain in the study and continue to be followed for safety related parameters according to the schedule of assessments.

All prior and concomitant medications will be listed by dose cohort and subject. Prohibited medications will be flagged in the listings.

In Mock Shell: Table 15.1.6 and Listing 16.2.4.1

6.8. Study Treatments

ADVM-043 is a genetically engineered, replication-incompetent, adeno-associated viral vector of serotype rh.10 (AAVrh.10), encoding human alpha-1 antitrypsin (A1AT complementary deoxyribonucleic acid (cDNA). Once thawed, ADVM-043 is a clear, colorless liquid.

In Part A of the study, ADVM-043 will be administered by IV up to 4 dose-levels.

- Cohort 1 ADVM-043 at 8×10^{13} vg
- Cohort 2 ADVM-043 at 4×10^{14} vg
- Cohort 3 ADVM-043 at 1.2×10^{15} vg
- Cohort 4 ADVM-043 at 4.8×10^{15} vg

Part B of the study was not continued and will be excluded from this analysis plan.

No subjects were enrolled into Cohort 4 of the study.

ADVM-043 exposure details will be listed by dose cohort and subject.

In Mock Shell: Listing 16.2.5

6.9. Efficacy Analysis

[REDACTED] All efficacy analysis will be based on FAS population.

6.9.1. Efficacy Endpoints

A descriptive summary of each of the below efficacy endpoints will be presented for actual results as well as change from baseline.

- Concentrations of total and M-specific A1AT over time

[REDACTED]

6.9.3. Biomarker Figures

Only the cumulative of positive pools (subtracting the medium) as mentioned in [section 5.4.13](#) will be plotted for [REDACTED] data in all figures below.

Bar Plot:

- Plasma Concentration of total A1AT will be plotted by week and subject to visualize the trend over weeks. X-axis will be week and Y-axis will be the total A1AT plasma concentration. Each bar represents a subject within each cohort. Each cohort will be presented in a separate figure.
- The same will be repeated for M-specific Plasma Concentration of A1AT.

[REDACTED]

Line Plot:

- Plasma Concentration of M-specific A1AT and ALT will be plotted together to visualize the change in M-specific A1AT along with ALT for each subject. X-axis will be week and Y-axis will be the M-specific A1AT plasma concentration for the bars and ALT for the line. Upper limit of Normal for ALT will also be presented as a reference line. Each subject will be presented in a separate figure.
- The same will be repeated for M-specific A1AT and [REDACTED]. X-axis will be week and Y-axis will be the M-specific A1AT plasma concentration for the bars and [REDACTED] for the line. Each subject will be presented in a separate figure.
- The same will be repeated for M-specific A1AT [REDACTED] value. X-axis will be week and Y-axis will be the M-specific A1AT plasma concentration for the bars [REDACTED]. Each subject will be presented in a separate figure.

In Mock Shell: Figure 14.2.5.1, Figure 14.2.5.2, Figure 14.2.5.3, Figure 14.2.5.4, Figure 14.2.5.5, Figure 14.2.5.6 and Figure 14.2.6.1.

6.10. Safety Analysis

The safety and tolerability of ADVM-043 are to be assessed by determining the frequency and percentages, severity, and relationship to study drug of AEs; and changes in the laboratory and other safety parameters (e.g., vital signs, ECG, etc.) by cohort. In addition, safety assessments will include urine pregnancy testing for women of childbearing potential. All safety data will be listed and summarized by cohort using the FAS population.

6.10.1. Adverse Events

An AE is any untoward medical occurrence in an enrolled subject regardless of its causal relationship to the IMP. A treatment-emergent adverse event (TEAE) is any event that does not present before exposure to the IMP or any event already present that worsens in either intensity or frequency after exposure to the IMP.

A summary of TEAEs will include numbers and percentages of subjects with TEAE, DLT, ADVM-043-related TEAE, Prednisone-related TEAE, TEAE \geq grade 3, serious TEAE, treatment-related serious TEAE and Fatal TEAE.

AEs are to be coded using the Medical Dictionary for Regulatory Activities (MedDRA) (Version 20.1) classification to give a preferred term (PT) and system organ class (SOC) for each event.

In Mock Shell: Table 14.3.1.1

6.10.1.1. Incidence of Treatment Emergent Adverse Events

Numbers and percentages of subjects with TEAEs will be presented. Summary of TEAEs will be presented by SOC and PT. These tables are to include overall totals for AEs within each organ class.

The incidence of TEAEs table will include only one occurrence of a preferred term (PT) per subject. If a subject report the same PT multiple times, then that the subject will be counted once under the

PT. If a subject report multiple TEAEs within the same SOC, then the subject will be counted once under that corresponding SOC.

The incidence of DLT will also be summarized by dose cohort and total in a similar manner.

Treatment related TEAEs will also be summarized by dose cohort and total as mentioned above. All AEs that are possibly, probably and definitely related to study treatment will be considered as treatment related TEAEs. Relationship to ADVM-043 and Prednisone will be presented separately.

All Adverse events will be listed by dose cohort and subject and TEAEs will be highlighted. All DLTs, Serious TEAEs and TEAEs leading to study discontinuation will also be listed individually.

Duration of AEs will be presented in the listing.

In Mock Shell: Table 14.3.1.2, Table 14.3.1.3, Table 14.3.1.4, Table 14.3.1.5, Listing 16.2.7.1, Listing 16.2.7.2 and Listing 16.2.7.3

6.10.1.2. Severity of Adverse Events

The intensity of the AE will be rated according to the Common Terminology Criteria for Adverse Events (CTCAE) version 4.03.

A summary of TEAEs by severity and dose cohort will be presented. If a subject reported multiple occurrence of the same TEAE, only the most severe occurrence will be presented.

In Mock Shell: Table 14.3.2.1

